5.3. Safety Analysis Set

The safety analysis set includes all enrolled patients who receive at least one dose of study medication.

5.4. Other Analysis Set

5.4.1. PK Analysis Set

The PK analysis set is defined as all treated patients who have at least 1 concentration of any of the study drugs. The PK parameter analysis population is defined as all treated patients who have at least one of the PK parameters of interest of any of the study drugs.

5.4.2. PD Analysis Set

The PD analysis set is defined as all enrolled subjects who receive at least 1 dose of PF-04449913 and have at least 1 pharmacodynamic parameter in active treatment period.

5.4.3. QTc-evaluable Analysis Set

The QTc-evaluable analysis set is defined as all patients who have baseline and at least one triplicate ECG assessment after having at least one PF-04449913 dose on study.

5.5. Treatment Misallocations

Not applicable.

5.6. Protocol Deviations

All deviations will be described in the CSR. Major deviations include, but are not limited to, administration of less than 80% of the planned dose during the DLT observation period of PF-04449913 or any component of the combination therapy [LDAC for Combination Cohort 1 (unfit patients), cytarabine/daunorubicin for Combination Cohort 2 (fit patients),

and azacitidine for Combination Cohort 3 (Azacitidine Combination)] for reasons other than drug related toxicity.

6. ENDPOINTS AND COVARIATES

The assessments on the day of the lead-in dose of PF-04449913 for Monotherapy Cohort and Combination Cohort 2 (Fit Patients) are considered baseline whenever they are available. The assessments on Cycle 1 Day 1 for Combination Cohort 1 (Unfit Patients), Expansion Cohort of LDAC combination for efficacy (Unfit Patients), Combination Cohort 3 (Azacitidine Combination) and Continuation Cohort are considered baseline whenever they are available. If not available, the assessment closest and prior to the lead-in dose (for Monotherapy Cohort and Combination Cohort 2) or Cycle 1 Day 1 [for Combination Cohort 1, Expansion Cohort of LDAC combination for efficacy (Unfit Patients), Combination Cohort 3 and Continuation Cohort] is considered baseline for patients in any arm, respectively.

6.1. Efficacy Endpoints (excluding the Continuation Cohort)

The efficacy endpoints of the disease response per investigator evaluation based on the Response Criteria CRF pages (see Protocol Appendix 5 through Appendix 9) is the primary method of documentation of disease. The response criteria differ for each hematologic malignancy (see [Appendix 2](#) through [Appendix 5](#) for details). Objective Response (OR) needs to be established before any subsequent documentation of progression.

The following dates are identified.

- The first objective response date: the assessment date of first documented objective response. However, these responses for MDS, CMML and CML need to be confirmed as described above.
- The first progression date: the assessment date of first documented (objective) disease progression.
- The first relapse date (except for CML): the assessment date of first documented relapse.
- The last disease assessment date: the date of last disease assessment date.

Combination Cohort 1 (Unfit Patients) and Expansion Cohort of LDAC combination for efficacy (Unfit Patients):

The following efficacy endpoints are defined.

DMR and its rate includes complete remission (CR), CR with incomplete blood count recovery (CRi), morphologic leukemia-free state (MLFS), marrow CR (mCR) and partial remission (PR) (see Protocol Appendix 5 and Appendix 8).

OS is defined as the time from the date of first dose of study drug to the date of death due to any cause. Patients last known to be alive will be censored at the date of last contact. The primary interest is the survival probability at 6 months and at 12 months.

Duration of response is only defined for patients who have ever achieved CR/CRi on study as the time from the date of first documentation of a CR/CRi (Protocol Appendix 5 and Appendix 8) to the date of loss of response after CR/CRi or death due to any cause. Duration of response data will be censored on the date of the last adequate response assessment for patients who do not have an event (loss of response or death). Duration of DMR for patients who have ever achieved DMR on study is also defined.

Time to response is only defined for patients who have ever achieved CR/CRi on study as the time from the date of first dose of study drug to the date of first documentation of a CR/CRi. Time to DMR for patients who have ever achieved DMR on study is also defined.

Transfusion independence is defined as follows taking into consideration of the schedule of activity described in Protocol. Transfusion history includes the transfusions prior to first dose of study treatment including Cycle 1 Day 1. Transfusion status on study includes the transfusions after first dose of study treatment.

- Independence of transfusion history for AML patients in Combination Cohort 1 (Unfit Patients) and Expansion Cohort of LDAC combination for efficacy (Unfit Patients) is defined as a lack of requirement for transfusion for at least 4 weeks;
- Independence of transfusion history for MDS patients is defined as a lack of requirement for transfusion for at least 8 weeks;
- Independence of transfusion status on study for AML and MDS patients is defined as a lack of requirement for transfusion for at least 8 weeks and ever met this definition after first dose of study treatment. Patients not followed by end of treatment for 8 weeks are not categorized as independent and dependent.

Combination Cohort 3 (Azacitidine Combination):

Same efficacy endpoints described in Combination Cohort 1 (Unfit Patients) will be defined. Note that only AML patients will be enrolled in this cohort.

The definition of transfusion independence of transfusion history is as follows:

- Independence of transfusion history in Combination Cohort 3 (Azacitidine Combination) is defined as a lack of requirement for transfusion for at least 8 weeks.

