 10. Adverse Event (AE) Assessments: Adverse events should be documented and recorded at each visit using NCI CTCAE version 4.0. Patients must be followed for AEs for 28 days after the last treatment administration or until all drug-related toxicities have resolved, whichever is later; or earlier than 28 days should the patient commence another anticancer therapy in the meantime. For SAEs, the active reporting period to Pfizer or its designated representative begins from the time that the patient provides informed consent, which is obtained prior to the patient's participation in the study, ie, prior to undergoing any study-related procedure and/or receiving investigational product, through and including 28 calendar days after the last administration of the investigational product. SAEs occurring to a patient after the active reporting period has ended should be reported to the Sponsor if the investigator becomes aware of them; at a minimum, all SAEs that the investigator believes have at least a reasonable possibility of being related to study drug are to be reported to the Sponsor. If the in-clinic study visits cannot be conducted due to COVID-19-related reasons, this assessment should be conducted by phone or video contact and based on the test results from a local clinic if applicable.
 11. Concomitant Medications and Treatments: Every concomitant medication and treatment required by the patient within 28 days prior to study drug treatment and during the trial (and up to 28 days following last treatment administration or until initiation of another oncologic treatment) must be reviewed. If the in-clinic study visits cannot be conducted due to COVID-19-related reasons, this review should be conducted by phone or video contact. After Protocol Amendment 8, these data are not required to be recorded on the CRF.
 12. All red blood cell and platelet transfusions, including date of each transfusion and the number of red blood cell units transfused will be recorded while on treatment. Note that number of units not number of bags must be recorded. For patients with high-risk MDS, the transfusion history must be provided for 8-weeks prior to the start of study treatment. If the in-clinic study visits cannot be conducted due to COVID-19-related reasons, this review should be conducted by phone or video contact. After Protocol Amendment 8, these data are not required to be recorded on the CRF.

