5.5. Concomitant Medication(s)

Concomitant treatment considered necessary for the patient's well-being may be given at discretion of the treating physician.

Every concomitant medication, blood products, and intervention (eg, paracentesis) required by the patient within 28 days prior to study drug treatment and during the trial (and up to 28 days following last treatment administration or until initiation of another oncologic treatment) and the reason for its administration, must be recorded on the CRF (After Protocol Amendment 8, these data are not required to be recorded on the CRF in the Expansion Cohort of LDAC combination for efficacy).

The following information is based on results from in vitro studies with PF-04449913 and a drug-drug interaction study with a strong CYP3A4/5 inhibitor in healthy subjects.

- **CYP3A4/5 Inhibitors:** In vitro studies with human liver microsomes and recombinant CYP enzymes indicated that PF-04449913 metabolism is primarily mediated by the drug-metabolizing enzyme CYP3A4/5. Clinically, there is likelihood that PF-04449913 plasma concentrations may be increased in the presence of co-administered inhibitors of the CYP3A4/5 enzymes. In a healthy volunteer study, ketoconazole, a potent CYP3A4/5 inhibitor, produced a 2.4-fold increase in plasma exposure and a 1.4-fold increase in peak plasma concentration of PF-04449913. Therefore a potential exists for drug-drug interactions with CYP3A4/5 inhibitors, and the use of strong/moderate CYP3A4/5 inhibitors are not permitted (unless approved by Sponsor) from 7 days prior to first dose of investigational product until study treatment discontinuation (eg, aprepitant, clarithromycin, cimetidine, ciprofloxacin, cyclosporine, diltiazem, erythromycin, tofisopam, verapamil, fluconazole, itraconazole, ketoconazole, and voriconazole). During this period, food, beverages, and herbal preparations which inhibit CYP3A4/5 are not permitted (eg, grapefruit juice). A comprehensive list of strong/moderate CYP3A4/5 inhibitors is provided in [Appendix 12](#) of the protocol. These requirements/lists may be updated based on emerging data;

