1. AMENDMENTS FROM PREVIOUS VERSION(S)

This Statistical Analysis Plan (SAP) v4 for study B1371005 is based on the protocol dated 21JAN2019 (protocol amendment 7) and the addition of the interim analysis. The analysis planned in SAP v4 will supersede the previous versions of the SAP and the statistical sections of the protocol.

Table 1. Summary of Major Changes in SAP Amendments

SAP Version	Change	Rationale
1	Not Applicable	Not Applicable
2	
 - Added the analysis plan of the 25 mg QD dose level in Monotherapy Cohort and amended the sample size of Monotherapy Cohort. - Added the analysis plan of the Combination Cohort 3. - Added the analysis plan of the Continuation Cohort. - Section 3 – Stated the timings of the primary and final analysis. - Section 6.1 – Added the definitions of the dates for the disease response. - Section 6.3.1 – Modified according to protocol amendment. - Section 7.4 – Conformed to Section 8.2.3.4 about analysis population. - Section 7.5 – Deleted the explanations of handlings of concentrations below/upper the limit of quantification. - Section 8.2.9.1.4 – Changed the definitions of the actual dose intensity and the relative dose intensities with reference to B1371003 - Section 8.2.9.1.4 – Added the listing of the actual dose intensity and the relative dose intensities with reference to B1371003 - Section 8.2.9.5 – Added the analysis plan of cytogenetics by European Leukemia Net. 	
 - Protocol amendment 3. - Protocol amendment 4. - Protocol amendment 5. - To clarify the timing of each analysis. - To include the dates related the efficacy as endpoints. - Protocol amendment 4. - Refer to Section 8.2.3.4. - Further amendment of SAP will be planned after investigation of handling of PD endpoints. - To unify the definition of these endpoints in Glasdegib program. - To unify the definition of these endpoints in Glasdegib program. - This characteristic is the prognostic factor for AML and will also be corrected in Phase 3 study for AML patients

	
 - Section 8.2.9.11 – Added the analysis plan of cardiac function evaluation - Section of Investigators Comments – This section was deleted 	
B1371019.
 
 - The analysis plan of this item was simply omitted. - This item is not included in analysis dataset.

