7.2. Efficacy Analysis

For efficacy analyses, no values will be imputed for missing data. Censoring for time-to-event endpoints is defined in [Section 6.1](#).

In the assessment of CR/CRi or DMR rate, patients who are not known to have achieved the endpoint of interest (CR/CRi or DMR) will be counted as non-responders.

7.3. PK

Concentrations Below the Limit of Quantification

In all data presentations (except listings), concentrations below the limit of quantification (BLQ) will be set to zero. (In listings BLQ values will be reported as “<LLQ”, where LLQ will be replaced with the value for the lower limit of quantification).

Deviations, Missing Concentrations and Anomalous Values

In summary tables and plots of median profiles, statistics will be calculated with concentrations set to missing if one of the following cases is true:

1. A concentration has been reported as ND (ie, not done) or NS (ie, no sample),
2. A deviation in sampling time is of sufficient concern or a concentration has been flagged anomalous by the pharmacokineticist.

Note that summary statistics will not be presented at a particular time point if more than 50% of the data are missing.

PK Parameters

Actual PK sampling times will be used in the derivation of PK parameters.

If a PK parameter cannot be derived from a subject's concentration data, the parameter will be coded as NC (ie, not calculated). (Note that NC values will not be generated beyond the day that a subject discontinues).

For evaluation of changes in pharmacokinetics of a compound when administered alone vs. in combination, only subjects with matching pair of pharmacokinetic assessments under both conditions will be included in the pharmacokinetic summary (ie, alone and in combination).

In summary tables, statistics will not be presented for a particular treatment group if more than 50% of the data are NC. For statistical analyses (ie, analysis of variance), PK parameters coded as NC will also be set to missing.

If an individual subject has a known biased estimate of a PK parameter (due for example to an unexpected event such as vomiting before all the drug is absorbed in the body), this will be footnoted in summary tables and will not be included in the calculation of summary statistics or statistical analyses.

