8.2.2.5. Transfusions

Analysis set: Full Analysis Set.

Table produced by: AML, MDS, irrespective of AML and MDS for Combination Cohort 1 (Unfit Patients), Expansion Cohort of LDAC combination for efficacy (Unfit Patients), and Combination Cohort 3 (Azacitidine Combination), respectively.

Tables:

For the transfusion independence, the transfusion history and transfusion status on study will be summarized in frequency tables as following.

Mock Table:

Number (%) of Subjects		n++
Transfusion Status on Study		
Independent		n+1 (n+1/n++)
Dependent		n+2 (n+2/n++)
Not Followed for 8 Weeks		n+3 (n+3/n++)
Transfusion History		
Independent		n1+ (n1+/n++)
Transfusion Status on Study		
Independent		n11 (n11/n1+)
Dependent		n12 (n12/n1+)
Not Followed for 8 Weeks		n13 (n13/n1+)
Dependent		n2+ (n2+/n++)
Transfusion Status on Study		
Independent		n21 (n21/n2+)
Dependent		n22 (n22/n2+)
Not Followed for 8 Weeks		n23 (n23/n2+)

Notation:

Transfusion History	Transfusion Status on Study			Total
	Independent	Dependent	Not Followed for 8 Weeks	
Independent	n11	n12	n13	n1+
Dependent	n21	n22	n23	n2+
Total	n+1	n+2	n+3	n++
				(Full Analysis Set)

Listings:

- Transfusion records including transfusion type, date of transfusion and number of units (Listing by dose level, cohort);

- Transfusion independence: transfusion history and transfusion status on study.

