8.2.3. Subset Analysis

Subset analyses will be performed for OS ([Section 8.2.2.4](#)) and transfusion independence ([Section 8.2.2.5](#)) based on the FAS for the subgroups defined below.

The following subgroups will be defined and used for analyses:

- DMR
 - DMR responder vs non-responder

Subset analyses for OS will use the primary censoring rules described in [Section 6.1](#). All the subgroup analyses are exploratory.

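### In the Expansion Cohort, the SAP's transfusion-independence window does not end when CRF recording of transfusions stops being required, so unrecorded treatment time can count as independence

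*SAP*

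**What the plan says.** **Definition.** SAP 6.1 uses one on-study rule for both diseases. Independence "is defined as a lack of requirement for transfusion for at least 8 weeks and ever met this definition after first dose". The one exclusion is "Patients not followed by end of treatment for 8 weeks are not categorized as independent and dependent". The mock table in SAP 8.2.2.5 accordingly has three on-study classes: independent, dependent, and not followed for 8 weeks. The source data are "Transfusion records including transfusion type, date of transfusion and number of units". SAP 8.2.3 repeats the table by "DMR responder vs non-responder". On missing data, SAP 7.2 says "For efficacy analyses, no values will be imputed for missing data".

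**Data collection.** For the Expansion Cohort, footnote 12 of protocol Table 3 (transfusions) ends: "After Protocol Amendment 8, these data are not required to be recorded on the CRF". Protocol 5.5, whose list includes blood products, adds: "After Protocol Amendment 8, these data are not required to be recorded on the CRF in the Expansion Cohort of LDAC combination for efficacy". Protocol 3.1.2 lets treatment run until progression or relapse, refusal or unacceptable toxicity, with no maximum number of cycles.

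**Versions.** SAP section 1 states that v4 is based on Amendment 7 of 21 January 2019 and that it supersedes the protocol's statistical sections. It has no rule for Amendment 8.

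**Survival.** Protocol Table 3 footnote 14, section 3.1.2 and section 5.3.7 drop survival follow-up in this cohort after Amendment 8. Deaths up to 28 days after last dose remain reportable (protocol 8.2). SAP 6.1 censors at last contact and puts primary interest on 6 and 12 months. SAP 8.2.2.4 also estimates 18-month survival and tabulates censoring reasons.

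**The concern.** Transfusions are dated event records. When nobody has to enter them, unrecorded time looks the same as transfusion-free time, and no missing value arises for SAP 7.2 to act on. The not-followed class does not catch this, because it is tied to the end of treatment and not to the end of recording. Because independence needs to be met only once, a single unrecorded 8-week stretch late in treatment is enough to move a patient from dependent to independent. The reverse cannot happen.

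The survival consequence is secondary. After Amendment 8, continued contact is required mainly for patients still on treatment, just off it, or with unresolved toxicity. Whether a patient is observed to 18 months can then depend on treatment status.

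**Working it through.** **1. The rule applied to one case.** A patient has been transfusion dependent since first dose and is treated for 56 days after Amendment 8. The site enters no transfusions.
- Followed for 8 weeks by end of treatment? Yes, so the exclusion does not apply.
- Any 8 weeks after first dose with no transfusion record? Yes, so the class is independent.
- Were transfusions given? The database cannot say.

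**2. Ceiling on the number of patients.** The documents supplied do not date Amendment 8, so its time A is varied, in months from the cohort's first dose. Accrual is 15 patients per year (SAP section 3), taken as uniform over 12 months. The window is w = 56/30.44 = 1.84 months. Time on treatment is assumed exponential with median m and rate λ = ln 2/m. The share treated at least 8 weeks past A is

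exp[−λ(A + w)] × [exp(12λ) − 1]/(12λ).

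- A = 20, m = 3: λ = 0.2310; 0.00643 × 5.41 = 3.5%, or 0.5 of 15.
- A = 20, m = 6: λ = 0.1155; 0.0802 × 2.164 = 17.4%, or 2.6 of 15.
- A mixture in which 34.1% of patients have m = 14 and the rest m = 2.5 gives 17.0% at A = 20, 13.4% at A = 24 and 9.7% at A = 30. With m = 3 the shares at A = 24 and 30 are 1.4% and 0.3%.

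The ceilings are therefore 0.5–2.6 patients (month 20), 0.2–2.0 (month 24) and under 0.1–1.5 (month 30).

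**3. Patients who would change class.** Those already independent cannot change. Their share s is not in the documents; 50% to 95% is assumed. The change probability per patient is q = ceiling share × (1 − s).
- A = 20, worst case: q = 0.174 × 0.5 = 0.087. Expected 1.3 patients; P(at least one) = 1 − 0.913^15 = 74%; P(at most one) = 62%.
- A = 20, best case: q = 0.035 × 0.05 = 0.0017. Expected 0.03; P(at least one) = 3%.
- A = 24: expected 0.01–1.0; P(at least one) = 1–65%.

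One patient is 1/15 = 6.7 points.

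**4. Survival: who could be affected.** With entries every 0.8 months (0 to 11.2), the number of patients who have not reached each landmark at Amendment 8 is:

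| Amendment 8 at month | 6 months | 12 months | 18 months |
|---|---|---|---|
| 19 | 0 | 6 | 13 |
| 21 | 0 | 3 | 11 |
| 24 | 0 | 0 | 7 |
| 27 | 0 | 0 | 3 |
| 29.2 | 0 | 0 | 0 |

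Only those also alive and off treatment lose required follow-up.

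**5. Survival: size.** Simulations set median survival to 8.3 or 8.8 months (protocol 1.2.8.1.3). They assumed median treatment of 3–6 months or the step 2 type of mixture, and varied off-treatment survival and death reporting. With off-treatment median survival of about 3 months or more, and deaths before the stop known at once, 18-month bias was −1.5 to +3.8 points (month 20), −0.9 to +0.9 (month 24) and about 0 (month 30). The extremes over all reporting assumptions were −2.6 to +7.7, −1.3 to +2.6 and −0.1 to +0.1. The sampling SD at n = 15 was 8.5–11 points. As a check, exponential survival with median 8.8 gives 0.242 at 18 months and √(0.242 × 0.758/15) = 11 points. Bias at 12 months was at most 2.4 points at month 20 and within 0.1 at month 24. At 6 months it was nil.

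**The case against.** The SAP says its transfusion definition takes account of the protocol's schedule of activities, so "followed" could be read as followed for transfusions, and a careful programmer would stop the window. That is reasonable, but nothing written requires it. Because entry is merely not required, sites may also differ in what they record.

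Anyone treated 8 weeks beyond month 20 has been on treatment for roughly 10 months or more and has probably met the definition already. This stands, and is why the likely count is none or one.

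A reader might infer three stronger things that the documents do not support:
- **That the responder subset is badly distorted.** With about 5 responders (0.341 × 15 = 5.1), one patient is 20 points. But protocol Appendix 8 already makes transfusion independence a condition of CR in AML, so responders are the less likely place for the error. Among about 10 non-responders, one patient is 10 points.
- **That 18-month survival is biased.** This needs patients who were alive, off treatment and short of 18 months at an undated amendment. Under planned accrual there are none from month 29.2. The direction also varies with how deaths are reported.
- **That survival needs a sensitivity analysis cut at Amendment 8.** With a stop at month 20, such an analysis could not estimate the 18-month rate in 45–51% of simulated cohorts. It left a residual of −3.0 to −0.4 points, similar in size to much of the bias it would be meant to show. SAP 8.2.2.4 already reports censoring reasons and lists each patient's censoring date.

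**Conclusion.** The transfusion point holds as a gap between SAP v4 and the current protocol. As written, the rule can turn unrecorded treatment time into transfusion independence, and only in that direction. The effect is probably none or one patient of 15. That rests on the assumed treatment durations, the unsourced 50–95% already independent, and an Amendment 8 date at or after about month 20. SAP section 1 describes the endpoint as exploratory.

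For survival, the most that can be said is that the 18-month rate can depend on treatment status. In every simulated scenario the bias stayed below the sampling SD at n = 15, and in most it was well below. The DMR test is unaffected. So is the rest of the primary analysis, due at about 12 + 8 × 28/30.44 = 19.4 months, unless Amendment 8 came earlier.

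**What to change.** In a SAP update:

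1. **Transfusions, Expansion Cohort.** Count only 8-week windows that end by the date required CRF transfusion recording stopped, taken as each site's Amendment 8 implementation date. Treat later time as not followed. Patients with under 8 weeks recorded by then go to the existing not-followed class. Under planned accrual that adds nobody if Amendment 8 came after month 12 + 1.84 = 13.8.
2. **Survival.** State in the report that 18-month survival can depend on treatment status after Amendment 8, using the censoring reasons already planned. No extra survival table is needed.
3. **Final analysis.** Reconcile the triggers. Apart from all patients having died, SAP section 3 uses 2 years after the last patient's first dose and protocol section 9 uses the last patient's last visit.

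The cost is a few sentences and one date per site. No new data are needed, and the primary test and the survival analysis stay as they are.
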